Session 1 (Baseline, Pre-Fitting). All testing will be completed separately in each ear for both groups. Otoscopy will be performed. The standard audiometric evaluation including air- and bone-conduction pure-tone audiometry; word-recognition in quiet (NU-6 words) and in noise (Words-in-Noise test; Wilson et al., 2003; Wilson, 2003; Wilson and Burks, 2005) will be completed. Tympanometry and aural acoustic reflexes also will be measured. These results will be compared to the audiogram for the original fitting to rule out a significant change in hearing. The current hearing aids will be maintained and the fit will be verified via real-ear measurements. The Client Oriented Scale of Improvement (COSI) will be completed to obtain the listening goals of the participant and to facilitate programming needs of the replacement hearing aids (e.g., whether or not manual programs are needed/desired) along with outcome measures for their current hearing aids (presented in random order). Obtaining subjective outcomes from their current hearing aids will provide baseline scores for which to compare outcomes from the replacement hearing aids to ensure the outcomes from the replacement hearing aids are at least equivalent. In addition, an intake form (See Appendix) will be completed for both groups to determine other device options and function (e.g., volume control options such as yes/no or unlinked/linked; removal filament or not; earmold style from previous order form; etc. The participant will be asked to demonstrate hearing aid skills with their current hearing aids. If questions or concerns arise, then they will be re-oriented during this session or disqualified. Earmold impressions will be taken for replacement hearing aids. For the BTE group, only acrylic earmold material will be used.

For both groups, RECD values will be obtained separately for each ear with the foam insert following the ANSI S3.46 (2013) standard as implemented in Audioscan Verifit 2 system. In

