Session 1 (Baseline, Pre-Fitting). The baseline testing for Session 1 of Study 3 is nearly identical to the procedures in Session 1 of Study 1. See Section 3g. Thus, only the minor differences will be described here. The comprehensive hearing evaluation, completion of the intake form (Appendix), and reorientation that is needed will be completed with the participant's current hearing aids. Their current hearing aids will be maintained and re-verified to ensure an accurate fit to prescriptive targets. The self-report outcome battery on the current hearing aids will be assessed (COSI, SADL, IOI-HA, and the aided portion 1 of the APHAB). Individual RECDs and REURs will be measured for each ear of each participant. The choice in replacement open vs closed domes will be made following routine clinical procedures. The receiver length will be measured and the dome size (open vs closed) will be estimated using manufacturer measurement tools. The replacement hearing aids will be ordered in ROES.

Session 2-The Intervention 'Visit'.

SoC-open and SOC-closed Group Fittings. These groups will receive the SoC, 30-minute face-to-face fitting appointment 4 weeks after Session 1, the average wait time for a fitting appointment. The right and left hearing aids will be programmed separately to the National Acoustics Laboratory Non-Linear 2 (NAL-NL2) prescription. The REAR of the hearing aids will be verified to the 50-, 65-, and 75-dB SPL prescriptive targets generated by the Verifit 2 system using the Speechmap™ stimulus. The criterion for an appropriate fitting would be ± 3 dB between the output and the prescriptive target from 250 Hz to the frequency in which the unaided threshold crossed the 65-dB SPL target. The real ear aided response for an 85 dB SPL input (REAR85) will be measured using an 85-dB SPL swept pure-tone to ensure that the maximum output of the hearing aids does not exceed the predicted uncomfortable loudness levels of the participant (feedback manager deactivated during this measurement only). The programming options will be optimized based on the information obtained on the intake form (Appendix). The participant will be provided with the manufacturer brochure and programming report from the manufacturer software. Consistent with current SoC, no orientation will be provided.

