EXP-open or EXP-closed Group Fittings. The participants in these groups will **not** be present during the fitting. These fittings will follow the same procedures as the testbox fittings in Study 1.

The only difference is the correction factors used will be determined from Study 2, and the measured RECD will be corrected as determined from study 2.

Two-Day Follow-Up Phone Call. All participants will receive a 2-day follow-up phone call after the hearing-aid fitting (either in situ fitting for SoC groups, or after delivery of hearing aid is confirmed with the delivery receipt for EXP groups) using the same telephone script (Appendix) as in Study 1.

Session 3-One-Month Post-Fitting. Session 3 procedures will be the same as in Session 3 in Study 1. In short, the self-report outcomes and exit interview will be assessed based on the patient experience of the replacement fittings. In addition, in situ REARs will be obtained from all groups using the current programming from the replacement aids. These in situ REARs will allow within and between group comparisons regarding the hearing-aid function and determine the accuracy of the experimental fittings relative to the SoC fittings. The repeat in situ REAR measurements in the SoC group (i.e., Sessions 2 and 3) will serve to assess the inherent variability with in situ REAR measurements and will facilitate interpretation of REAR data when comparing the accuracy of the in situ and derived REARs in the experimental groups.

Adverse Events

Given the study population (healthy Veterans with no more than a moderate sensorineural hearing loss), who are obtaining replacement hearing aids (Study 1 and 3), there are very few unexpected or anticipated serious events. In rare cases, ear injury during an earmold impression procedure could occur (Study 1 only), or occasional mild discomfort during probe microphone measurements (Studies 1, 2, and 3). Otherwise, participants may experience boredom or frustration with the taking a hearing test, listening to speech, or completing study questionnaires. All adverse events will be reported per Durham VAMC requirements. All Serious, Unanticipated and Related adverse events will be reported to IRB within 5 business days of hearing of the event. All other adverse events will be reported at continuing review.

Costs and/or Payments to Subjects

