Study 3 Data Analysis. We will use a similar data analysis plan as in Study 1 for real ear/fitting accuracy variables. This will determine if derived REARs from open-fit RECD-fittings will accurately meet prescriptive targets and expected aided audibility and if *in situ* REARs of RECD-fittings are equivalent to *in situ* REARs in SoC fittings of open-fit styles. For statistical reasons, we propose to complete separate analyses for the left and right REAR data as described in Experiment 1. For self-report data, a separate mixed model repeated measures ANOVA will be conducted to compare outcomes amongst the groups. This will determine if subjective self-report outcomes across a variety of domains differs as a function of fitting experience and open-fit style.

The data will be analyzed by the PI; her collaborator and co-investigator ([name]., at Vanderbilt University—coded data only) who also will develop the correction factors; and the statistical consultant at Duke University (to be determined). A copy of coded data only will be

stored on the Duke University Server. A copy of all electronic data will also be stored at VA on \\v06.med.va.gov\\dur\\Research\\Research\\[name].

Privacy, Confidentiality, and Information Security

1. Lists of Data Reviewed and/or Collected for Screening/Recruitment and Conduction of Study:

It will be obtained, used, and/or shared for this study includes:

Identifier(s)	Source(s) of Health Information
 Names	 Medical history & physical exam information
 All geographic subdivisions smaller than a State, including street address, city, county, precinct, and zip code. Describe: mailing address	 Photographs, videotapes, audiotapes, or digital or other images
 All elements of dates (except year) for dates directly related to an individual, including birth date, admission date, discharge date, visit or treatment dates, etc.; and all ages over 89, Describe: age, audiology treatment dates (hearing test dates, fitting dates)	 Biologic specimens (e.g., blood, tissue, urine, saliva). Describe:
 Telephone numbers	 Progress notes
 Fax numbers	 Diagnostic / Laboratory test results

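### Study 3 self-report analysis states no adjustment for the Session 1 scores already collected; adding it is expected to sharpen the EXP v SoC comparison within coupling (optional, near-costless)

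*Combined protocol and SAP*

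**What the plan says.** The Study 3 Data Analysis section gives the self-report analysis in two sentences: "For self-report data, a separate mixed model repeated measures ANOVA will be conducted to compare outcomes amongst the groups", and "This will determine if subjective self-report outcomes across a variety of domains differs as a function of fitting experience and open-fit style". The carry-over from the Study 1 plan in the same section covers only real-ear and fitting-accuracy variables.

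The scores needed for adjustment are already collected. Study 3, Session 1: "The self-report outcome battery on the current hearing aids will be assessed (COSI, SADL, IOI-HA, and the aided portion 1 of the APHAB"). Study 3, Session 3: "Session 3 procedures will be the same as in Session 3 in Study 1", and "In short, the self-report outcomes and exit interview will be assessed based on the patient experience of the replacement fittings". The Study 1 Session 3 list contains the COSI, the second aided portion of the APHAB, the IOI-HA and the SADL.

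Two places hint that Session 1 may be meant to enter the model. Study 1, Session 1 gives a purpose for the baselines: "Obtaining subjective outcomes from their current hearing aids will provide baseline scores for which to compare outcomes from the replacement hearing aids". Study 3, Session 1 then says: "The baseline testing for Session 1 of Study 3 is nearly identical to the procedures in Session 1 of Study 1". The Study 1 Data Analysis Plan uses a model of the same name to compare groups and also current with replacement fittings. Neither study states Session 1 as a covariate.

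On allocation, the Design section calls Study 3 quasi-random, describes random assignment to four groups based on coupling, and compares each experimental fitting with its SoC counterpart. The dome type itself is a clinical decision: "The choice in replacement open vs closed domes will be made following routine clinical procedures".

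**The concern.** A reader cannot tell from the plan which EXP v SoC test will be run. If session is the repeated factor, the usual test is group-by-session, which is a comparison of change scores. If only subscale is repeated, the Session 1 scores go unused. Under random assignment within coupling either test is valid, but covariate adjustment is generally more precise than both.

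Precision matters here because Study 3 was sized on fitting accuracy, and no power is stated for self-report. Each within-coupling comparison rests on 19 v 19 evaluable participants. Hypothesis 3b predicts no significant difference, so a wide interval could leave a real worsening with mailed fittings undetected.

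**Working it through.** **Inputs from the documents.** Study 3 Power Analysis: 152 ears / 2 = 76 participants; 76 / 4 = 19 per group; 76 + 12 = 88 enrolled, 22 per group. These counts are internally consistent. They rest on fitting accuracy, so there is no self-report power or interval width to reproduce.

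**Assumptions, none of them in the documents.** Correlation r between Session 1 and Session 3 scores; s = Session 1 SD / Session 3 SD; a true difference of 0.5 Session 3 SD for the power figures; one subscale score at a time. All figures below use one model: four groups of 19, with 76 − 4 = 72 residual df before adjustment and 71 after.

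**Variance factors** (Session 3 SD = 1):
- Session 3 only: 1
- Change score (group-by-session): 1 + s² − 2rs
- Adjusted: (1 − r²) × 1.0143, where 1 + 1/(72 − 2) = 1.0143 is the cost of estimating the slope

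**Break-even points.** Against Session 3 only: r = √(1 − 1/1.0143) = 0.119. Against change with s = 1: 2(1 − r) = (1 − r²) × 1.0143 gives r = 2/1.0143 − 1 = 0.972.

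**Within coupling, 19 v 19, s = 1, r = 0.5.**
- Unadjusted SE = √(2/19) = 0.3244; half-width = 1.9935 × 0.3244 = 0.647. The change test gives the same value here, since 2(1 − 0.5) = 1.
- Adjusted factor = 0.75 × 1.0143 = 0.7607; SE = 0.3244 × √0.7607 = 0.2830; half-width = 1.9939 × 0.2830 = 0.564.
- Power for 0.5 SD (two-sided 5%, noncentral t): noncentrality 0.5/0.3244 = 1.54 on 72 df gives 0.33; 0.5/0.2830 = 1.77 on 71 df gives 0.41.
- Averaged over couplings (38 v 38): half-width 0.457 to 0.399, power 0.58 to 0.69.

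**Across r, s = 1, within-coupling half-width in SD:**

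| r | Session 3 only | Change | Adjusted | v Session 3 only | v change |
|---|---|---|---|---|---|
| 0.3 | 0.647 | 0.765 | 0.622 | −3.9% | −18.8% |
| 0.5 | 0.647 | 0.647 | 0.564 | −12.8% | −12.8% |
| 0.7 | 0.647 | 0.501 | 0.465 | −28.1% | −7.1% |
| 0.8 | 0.647 | 0.409 | 0.391 | −39.6% | −4.4% |

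**Unequal SDs, adjusted v change.**
- s = 0.8, r = 0.5: 0.7607 v 0.84, about 5% narrower.
- s = 0.8, r = 0.7: 0.5173 v 0.52, about 0.2% narrower.
- s = 0.7, r = 0.7: 0.5173 v 0.51, about 0.7% wider.
- s = 1.25, r = 0.5: 0.7607 v 1.3125, about 24% narrower.

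**Averaging over subscales.** With an assumed four subscales, inter-subscale correlation ρ and cross-session correlation between different subscales of rρ, every variance is multiplied by (1 + 3ρ)/4, which is 0.625 at ρ = 0.5 and 0.775 at ρ = 0.7. Both half-widths shrink by the square root of that (0.791 or 0.880), so the proportional gain is unchanged.

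**Missing baselines.** If 10% of Session 1 scores were missing and those participants were dropped, efficiency relative to a Session 3-only analysis of everyone would be 0.9/(0.91 × 1.0143) = 0.975 at r = 0.3, a small loss. At r = 0.5 it would be 0.9/0.7607 = 1.18 instead of 1/0.7607 = 1.31.

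**The case against.** The best defence is that Session 1 may already be used. The same battery is given twice, the model is a repeated measures one, and the Study 1 model of the same name compares current with replacement fittings. On that reading the gain is only over a change-score test: 7% at r = 0.7, 4% at r = 0.8, and none at s = 0.7 with r = 0.7. This stands as a limit on size. It does not remove the point, because the Study 3 text does not say so and adjustment still does at least about as well over most plausible values.

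The gain over Session 3 only may also be modest, since the two sessions rate different devices; at r = 0.3 it is 4%. That stands too.

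The change is not wholly free. The Risk/Benefit Assessment lets participants skip questionnaire items, so a plain covariate model could lose people. The fix therefore needs a rule for missing baselines.

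Finally, the plan states a test of difference for self-report and no interval or margin. Adjustment sharpens that test, but it does not supply the missing margin.

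A reader might go further and infer that the planned analysis is biased, that Session 1 is ignored, or that the interval is certain to narrow. The documents support none of these. Both candidate tests are unbiased under random assignment, the use of Session 1 is unstated rather than excluded, and r and the SDs are not given.

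**Conclusion.** The point holds as an optional improvement. No Session 1 adjustment is stated for Study 3 self-report, and adding it is expected to improve precision for EXP v SoC within coupling, provided that assignment is random. The gain holds against Session 3 only for r above about 0.12 and, with equal SDs, against a change-score test for r up to about 0.97. The illustrative size at r = 0.5, a within-coupling half-width about 13% narrower, rests on an assumed correlation and equal SDs; the effect against a change-score test ranges from useful to slightly negative as the SD ratio varies.

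Two extensions would be wrong. A narrower interval does not by itself establish equivalence for Hypothesis 3b. Nor does the argument reach open v closed: dome type is chosen clinically, so baseline adjustment does not make that comparison a randomised one.

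**What to change.** In the Study 3 Data Analysis section, for each of the SADL, IOI-HA and APHAB:

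- Keep the mixed model with subscale as the repeated factor. Take Session 3 scores as the outcome and add the participant's Session 1 score on the same subscale as a covariate.
- Include fitting approach, coupling and their interaction. Name EXP v SoC within coupling, and its average over couplings, as the test terms, each with a 95% confidence interval. State how multiplicity over instruments and contrasts is handled.
- Keep participants with a missing Session 1 score, either through a two-session model that holds Session 1 means equal for EXP and SoC within coupling, or through a simple prespecified baseline imputation rule.
- Label open v closed as a non-randomised comparison, and keep COSI change ratings outside this model. Change from current to replacement aids can still be described by group.

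The cost is a short SAP edit and about one degree of freedom per covariate slope. No new data, visits or changes to fitting are needed.
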